### 8.3 Technical Computational Details for Primary and Secondary Analysis

(1) Two samples/aliquots of blood will be collected for serum creatinine assessments. While one blood sample will be analyzed by the central laboratory as soon as it is received and accessioned, the other one will be frozen and later batched analysis when a subject completes all his/her serum creatinine blood draws needed in the protocol. This batched assessment of serum creatinine is considered to have less intra-subject variation, and will be used for the eGFR derivations for the efficacy analysis. Since it is expected that two different methods are applied to these two sets of blood samples (enzymatic method to the batched sample and rate blank method to the first sample), these two sets of eGFR data are not interchangeable. In addition, the eGFR labeled as “Unscheduled” will be used in efficacy analysis if a subject has two eGFRs observed on the same day and same time.

██  
██  
██

[REDACTED]

Or

[REDACTED]

- (3) The following SAS codes will be used for the primary analyses:

```
PROC GLM;  
  CLASS TREATMENT AGE_STATUS GFR_STATUS TKV_STATUS;  
  WEIGHT WEIGHT;  
  MODEL ANNUALIZED_CHANGE = TREATMENT BASELINE AGE_STATUS  
                                GFR_STATUS TKV_STATUS;  
RUN;
```

- (4) The SAS code of the sensitivity analysis of the primary endpoint specified in [Section 8.1.2](#) is

```
PROC MIXED EMPRICAL;  
  CLASS SUBJECT TREATMENT AGE_STATUS GFR_STATUS TKV_STATUS;  
  MODEL GFR = TREATMENT TIME TREATMENT*TIME BASELINE  
              AGE_STATUS GFR_STATUS TKV_STATUS;  
  RANDOM INTERCEPT ITIME/TYPE=UN SUB=SUBJECT G;  
RUN;
```

If the model has any convergence problem, the variables of AGE\_STATUS, GFR\_STATUS, and TKV\_STATUS may be dropped out of the model.

- (5) The SAS code of the analysis of the key secondary endpoint specified in [Section 8.2.1](#) is

```
PROC MIXED EMPRICAL;  
  CLASS SUBJECT TREATMENT AGE_STATUS GFR_STATUS TKV_STATUS;  
  MODEL GFR = TREATMENT TIME TREATMENT*TIME BASELINE  
              ACUTE_HEMODYNAMIC_EFFECT AGE_STATUS GFR_STATUS  
              TKV_STATUS;  
  RANDOM INTERCEPT ITIME/TYPE=UN SUB=SUBJECT G;  
RUN;
```

If the model has any convergence problem, the variables of AGE\_STATUS, GFR\_STATUS, and TKV\_STATUS may be dropped out of the model.

(6) The on-treatment visits included in the sensitivity analysis of the key secondary endpoint mentioned in Section 8.2.2 are Months [REDACTED]. The mean value of these visits in months is 6.5. For a new numerical axis with its original falling at 6.5 months, the 12 original time points will become [REDACTED] on this numerical axis. Thus the coefficients of the linear trend contrast of these 12 months are [REDACTED]. With treatment be coded, for example, as 0 for placebo and 1 for tolvaptan, the SAS code for the analysis of the key secondary endpoint is

```

PROC MIXED ;
  CLASS TREATMENT VISIT AGE_STATUS GFR_STATUS TKV_STATUS
  SUBJECT ;
  MODEL CHANGE = TREATMENT VISIT TREATMENT*VISIT BASELINE
  BASELINE*VISIT AGE_FACTOR GFR_FACTOR TKV_FACTOR ;
  REPEATED VISIT / TYPE=UN SUB=SUBJECT ;
  LSMEANS TREATMENT*VISIT / PDIFF CL ALPHA=0.05 ;
  ESTIMATE 'TREND DIFF' TREATMENT 0 0
  VISIT 0 0 0 0 0
  TREATMENT*VISIT [REDACTED]
  ;
RUN ;

```

If the estimate statement is not estimable, the fixed effects of AGE\_STATUS, GFR\_STATUS, and TKV\_STATUS may be dropped out of the model. In addition, 6/143 will be multiplied to the estimate of the linear trend contrast in order to provide an estimate of treatment difference in eGFR slope.

In case there is a convergence problem in the MMRM model with the unstructured variance covariance matrix, the following variance covariance matrix structures will be used in the order of 1) heterogeneous toeplitz, 2) heterogeneous autoregressive of order 1, 3) heterogeneous compound symmetry, 4) autoregressive of order 1, and 5) compound symmetry. The first (co)variance structure which does not have convergence problem will be the one used for the analysis. If a structured covariance has to be used, the “sandwich” estimator of the variance covariance matrix of the fixed effects parameters will be used in order to deal with possible model misspecification of the covariance matrix.

(7) For a tolvaptan subject who have IMP interruption during the trial, if the subject have eGFR observed during the interruption and the eGFR observation is more than one week from the last IMP dose before the interruption, the eGFR observation will be flagged (yes=1 and no = 0) with a tolvaptan hemodynamic effect and included in the key secondary analysis. If the observation is less than one week but more than 24 hours from

the last IMP dose before the interruption, the observation will be excluded from the key secondary analysis.

(8) Observations in eGFR which are 50% larger than a subject's screening eGFR observations will be excluded from the primary and second efficacy analyses.

(9) The following method to derive the weight for the primary analysis is proposed if the number of eGFR observations is kept at 3 in the pre-treatment baseline period. In order to derive the weight used in the weighted analysis, the following model is considered:

$$y_{i,0,k} = \alpha_i + e_{i,0,k} \quad \text{where } k = 1, 2, K_{i,0} \quad (1)$$

$$y_{i,j,k} = \alpha_i + \delta_{i,j} + e_{i,j,k} \quad \text{where } k = 1, 2, K_{i,j} \quad (2)$$

where  $K_{i,0}$  is the number of eGFR observations during the pre-treatment baseline period for subject  $i$ , and  $K_{i,j}$  is the number of eGFR observations during the post-treatment follow-up period for subject  $i$ , with visit  $j$  as the visit Month 12 for completers or mapped regular visits for early dropouts.  $\alpha_i$  is a random variable for the "real" eGFR baseline of subject  $i$ , and this variable will be cancelled out for change from baseline.  $\delta_{i,j}$  is a random variable for change from pre-treatment baseline for subject  $i$  to visit  $j$ . These  $\delta_{i,j}$ s are normally distributed, with means being  $\delta_{p,j}$  for placebo subjects and  $\delta_{T,j}$  for tolvaptan subjects, and variance  $\sigma_{\delta,j}^2$ . These  $\delta_{i,j}$ s are supposed to be independent from subject to subject, and each subject has only one post-baseline visit  $j$  in the primary analysis. In addition,  $\alpha_i$ s are assumed iid normally distributed,  $e_{i,j,k}$  are assumed iid  $N(0, \sigma^2)$ , and all these random variables are mutually independent. Their average over the  $K_{i,0}$  observations at baseline and the  $K_{i,j}$  observations at post-treatment follow-up will be:

$$\bar{y}_{i,0} = \alpha_i + \bar{e}_{i,0}, \quad \text{where } \bar{e}_{i,0} \sim N(0, \sigma^2/K_{i,0}) \quad (3)$$

$$\bar{y}_{i,j} = \alpha_i + \delta_{i,j} + \bar{e}_{i,j}, \quad \text{where } \bar{e}_{i,j} \sim N(0, \sigma^2/K_{i,j}) \quad (4)$$

the distribution of their difference is:

$$\bar{y}_{i,j} - \bar{y}_{i,0} = \delta_{i,j} + \bar{e}_{i,j} - \bar{e}_{i,0} \sim N(., \sigma_{\delta,j}^2 + \sigma^2(1/K_{i,0} + 1/K_{i,j})), \quad (5)$$

where the mean of the normal distribution is  $\delta_{p,j}$  for placebo subjects and  $\delta_{T,j}$  for tolvaptan subjects.

In order to estimate the variance components given in (5), a further assumption of all  $\sigma_{\delta,j}^2$ 's are equal, ie,  $\sigma_{\delta,j}^2 = \sigma_{\delta}^2$  is made, since there may not be enough subjects withdraw to stabilized the estimate of  $\sigma_{\delta,j}^2$  at some visits. In addition, it is assumed all subjects get 3 eGFR observations at baseline. This assumption is reasonable, since usually subjects follow protocol schedules more strictly at the beginning of the trial, and could simplify

the estimation of the variance components. Then, a formula of change from baseline can be written similar to (5) for the estimation of the variance components:

$$y_{i,j,k} - \bar{y}_{i,0} = \delta_{i,j} + e_{i,j,k} - \bar{e}_{i,0} \sim N(., \sigma_{\delta}^2 + \sigma^2(1 + 1/3)), \quad (6)$$

A mixed model with fixed effect factors of treatment nested within visit, replication (for the repeated observations at the post-treatment follow-up in eGFR) will be applied to change from baseline (as the average of the 3 pre-treatment eGFR observations) in eGFR observed at each replication. In this mixed model, replications at the post-treatment follow-up are considered as the repeated measurements, with a compound symmetric variance matrix structure. In this estimated variance-covariance matrix, the diagonal elements are the estimate of  $\sigma_{\delta}^2 + \sigma^2(1 + 1/3)$ , and the off diagonal elements are the estimate of  $\sigma_{\delta}^2 + \sigma^2(1/3)$ . Solving these two equations will get the estimates of  $\sigma_{\delta}^2$  and  $\sigma^2$ . With these variance component estimates, the variance given in formula (5) is estimated for each subject. Dividing the estimated variance given in (5) by the subject's trial duration will provide an estimated variance for the subject's annualized change in eGFR. The inverse of this estimated variance will be the weight of the subject used in the primary analysis.

SAS code for the estimation of variance component

```
PROC MIXED ;
  CLASS SUBJECT VISIT TREATMENT REPLICATION ;
  MODEL CHANGE = TREATMENT (VISIT) REPLICATION ;
  REPEATED REPLICATION / TYPE=CS SUB=SUBJECT ;
RUN ;
```

In this estimation of variance components, it is assumed the post-treatment follow-up eGFR observations of early withdrew subjects are mapped into scheduled visits. Since the monthly scheduled visits in this protocol, for a subject early withdrew IMP, compared to the subject's last scheduled on-treatment visit, if the first post-treatment follow-up eGFR is observed less or equal to 25 days (= 15 + 7 + 3) after the last scheduled on-treatment visit, then the subject's post-treatment follow-up eGFR observations will be mapped to the subject's last scheduled on-treatment visit; otherwise, if the first post-treatment follow-up eGFR is observed less or equal to 55.5 days (= 30.5 + 15 + 7 + 3) after the last scheduled on-treatment visit, then the subject's post-treatment follow-up eGFR observations will be mapped to one month after the subject's last scheduled on-treatment visit; etc.

(10) The following method to derive the weight for the primary analysis is proposed in case the blinded sample size re-estimation leads to a change in the number of eGFR observations in pre-treatment baseline period, so that the assumption of equal number of pre-treatment baseline eGFR observations is no longer.

In order to derive the weight used in the weighted analysis, the following model is considered:

$$y_{i,0,k} = \alpha_i + e_{i,0,k} \quad \text{where } k = 1, 2, K_{i,0} \quad (1)$$

$$y_{i,1,k} = \alpha_i + \delta_i + e_{i,1,k} \quad \text{where } k = 1, 2, K_{i,1} \quad (2)$$

where  $K_{i,0}$  is the number of eGFR observations during the pre-treatment baseline period for subject  $i$ , and  $K_{i,1}$  is the number of eGFR observations during the post-treatment follow-up period for subject  $i$ , whether subject  $i$  completes the study or not.  $\alpha_i$  is a random variable for the “real” eGFR baseline of subject  $i$ , and this effect will be cancelled out for change from baseline.  $\delta_i$  is a random variable for the “real” change from baseline to post-treatment follow-up of subject  $i$ . These  $\delta_i$ s are normally distributed, with a common variance  $\sigma_\delta^2$ , and are independent from subject to subject. In addition,  $\alpha_i$ s are assumed iid normally distributed,  $e_{i,1,k}$  are assumed iid  $N(0, \sigma^2)$ , and all these random variables are mutually independent. Their average over the  $K_{i,0}$  observations at baseline and the  $K_{i,1}$  observations at post-treatment follow-up will be:

$$\bar{y}_{i,0} = \alpha_i + \bar{e}_{i,0}, \quad \text{where } \bar{e}_{i,0} \sim N(0, \sigma^2/K_{i,0}) \quad (3)$$

$$\bar{y}_{i,1} = \alpha_i + \delta_i + \bar{e}_{i,1}, \quad \text{where } \bar{e}_{i,1} \sim N(0, \sigma^2/K_{i,1}) \quad (4)$$

the distribution of the change from baseline for subject  $i$  is:

$$\bar{y}_{i,1} - \bar{y}_{i,0} = \delta_i + \bar{e}_{i,1} - \bar{e}_{i,0} \sim N(., \sigma_\delta^2 + \sigma^2(1/K_{i,0} + 1/K_{i,1})) \quad (5)$$

The estimation of  $\sigma^2$  is simply provided by:

$$v_e = \frac{1}{2} \{ \sum_i \sum_k (y_{i,0,k} - \bar{y}_{i,0})^2 / \sum_i (K_{i,0} - 1) + \sum_i \sum_k (y_{i,1,k} - \bar{y}_{i,1})^2 / \sum_i (K_{i,1} - 1) \} \quad (6)$$

where  $\sum_i$  sums over all subject  $i$ , and  $\sum_k$  sums over all replicate  $k$  for subject  $i$ , either at baseline visit or post-treatment follow-up visit. Let

$$d_i = (\bar{y}_{i,1} - \bar{y}_{i,0}) / t_i \sim N(., [\sigma_\delta^2 + \sigma^2(1/K_{i,0} + 1/K_{i,1})] / t_i^2) \quad (7)$$

being the annualized change from baseline of subject  $i$  and its distribution, where  $t_i$  is the trial duration to annualize the primary endpoint for subject  $i$ , with mean  $\beta_T$  and  $\beta_P$  for tolvaptan and placebo subjects respectively. Let

$$\tau_i = [\sigma_\delta^2 + \sigma^2(1/K_{i,0} + 1/K_{i,1})] / t_i^2 \quad (8)$$

The treatment averages are:

$$\bar{d}_T = \sum_{i \text{ in TLV}} d_i / n_T \quad \text{and} \quad \bar{d}_P = \sum_{i \text{ in PLC}} d_i / n_P \quad (9)$$

where  $\sum_{i \text{ in TLV}}$  ( $\sum_{i \text{ in PLC}}$ ) sums over all tolvaptan (placebo) subjects, and  $n_T$  ( $n_P$ ) is the total number of subjects in tolvaptan (placebo). Let

$$v = \frac{1}{2} \{ \sum_{i \text{ in TLV}} (d_i - \bar{d}_T)^2 / (n_T - 1) + \sum_{i \text{ in PLC}} (d_i - \bar{d}_P)^2 / (n_P - 1) \} \quad (10)$$

Since

$$\begin{aligned} \sum_{i \text{ in TLV}} (d_i - \bar{d}_T)^2 &= \sum_{i \neq i' \text{ in TLV}} (d_i - d_{i'})^2 / 2n_T \text{ and} \\ \sum_{i \text{ in PLC}} (d_i - \bar{d}_P)^2 &= \sum_{i \neq i' \text{ in PLC}} (d_i - d_{i'})^2 / 2n_P \end{aligned} \quad (11)$$

formula (10) can be rewritten as:

$$v = \sum_{i \neq i' \text{ in TLV}} (d_i - d_{i'})^2 / [4n_T(n_T - 1)] + \sum_{i \neq i' \text{ in PLC}} (d_i - d_{i'})^2 / [4n_P(n_P - 1)] \quad (12)$$

and

$$\begin{aligned} E(v) &= \sum_{i \neq i' \text{ in TLV}} (\tau_i + \tau_{i'}) / [4n_T(n_T - 1)] + \sum_{i \neq i' \text{ in PLC}} (\tau_i + \tau_{i'}) / [4n_P(n_P - 1)] \\ &= \sum_{i \neq i' \text{ in TLV}} \{ [\sigma_\delta^2 + \sigma^2(1/K_{i,0} + 1/K_{i,1})] / t_i^2 + [\sigma_\delta^2 + \sigma^2(1/K_{i',0} + 1/K_{i',1})] / t_{i'}^2 \} / [4n_T(n_T - 1)] \\ &+ \sum_{i \neq i' \text{ in PLC}} \{ [\sigma_\delta^2 + \sigma^2(1/K_{i,0} + 1/K_{i,1})] / t_i^2 + [\sigma_\delta^2 + \sigma^2(1/K_{i',0} + 1/K_{i',1})] / t_{i'}^2 \} / [4n_P(n_P - 1)] \\ &= \sum_{i \text{ in TLV}} \{ [\sigma_\delta^2 + \sigma^2(1/K_{i,0} + 1/K_{i,1})] / t_i^2 \} / (2n_T) + \sum_{i \text{ in PLC}} \{ [\sigma_\delta^2 + \sigma^2(1/K_{i,0} + 1/K_{i,1})] / t_i^2 \} / (2n_P) \\ &= \delta^2 [\sum_{i \text{ in TLV}} 1 / (2n_T t_i^2) + \sum_{i \text{ in PLC}} 1 / (2n_P t_i^2)] \\ &+ \sigma^2 [\sum_{i \text{ in TLV}} (1/K_{i,0} + 1/K_{i,1}) / (2n_T t_i^2) + \sum_{i \text{ in PLC}} (1/K_{i,0} + 1/K_{i,1}) / (2n_P t_i^2)] \end{aligned} \quad (13)$$

where  $E(v)$  is the expectation of  $v$ . Thus, the estimate of  $\sigma_\delta^2$  is:

$$\begin{aligned} v_\delta &= \{ v - v_e [\sum_{i \text{ in TLV}} (1/K_{i,0} + 1/K_{i,1}) / (2n_T t_i^2) + \sum_{i \text{ in PLC}} (1/K_{i,0} + 1/K_{i,1}) / (2n_P t_i^2)] \\ & / [\sum_{i \text{ in TLV}} 1 / (2n_T t_i^2) + \sum_{i \text{ in PLC}} 1 / (2n_P t_i^2)] \} \end{aligned} \quad (14)$$

And the estimated variance of the annualized change from baseline for subject  $i$  ( $d_i$ ) is:

$$[v_\delta + v_e (1/K_{i,0} + 1/K_{i,1})] / t_i^2 \quad (15)$$

The reciprocal of (15) will be the weight for subject  $i$  used in the weighted analysis.

(11) Mapping of unscheduled visit and end of treatment visit during double-blind treatment period to nominal visits: In general, these visits will be mapped into the monthly nominal visits based on the mid-point between two monthly visits, ie, if an unscheduled visit or an end of treatment visit is within 15 days of the previous visit, it will be mapped to the previous visit; if it is greater than 15 day of the previous visit, it will be mapped to next appropriate visit, with 30.5 days (round if necessary) between each two adjacent nominal visits. If an unscheduled visit or an end of treatment visit falls into 351 (rounded from 30.5x11 + 15) to 381 (= 366 + 15) days post-randomization, it

will be mapped to visit Month 12. If an unscheduled visit or an end of treatment visit is more than 2 days post last dose, it will not be mapped to these double-blind nominal visits, but will be considered for the post-treatment follow-up visits, if it falls within 7 to 40 days from the last dose of IMP.

(12) The following reasons are collected in the CRF for subjects who discontinue IMP:

1. Discontinued based on subject decision:
  - 1.1. IMP not tolerable (AE which is annoying or uncomfortable but not serious or hazardous)
  - 1.2. Reason other than tolerability
    - 1.2.1. Pregnancy
    - 1.2.2. Trial too burdensome
    - 1.2.3. Other reason
  - 1.3. Taking marketed product for tolvaptan
2. Discontinued based on physician decision
  - 2.1. Potential IMP-related safety concern or serious AR placing subject at undue hazard
  - 2.2. Progression of disease leading to dialysis, transplantation or eGFR decline
  - 2.3. Hepatic AE
3. Other
  - 3.1. Subject death
  - 3.2. Subject lost to follow-up

In [Section 8.2.4](#) for sensitivity analysis including imputation of missing data, six reasons of discontinuation of IMP were listed in the order of their likelihood to be MNAR. The mapping of the reasons of discontinuation of IMP to the reasons used in the sensitivity analysis is provided below:

- Progression of renal disease or Lack of efficacy: Item 2.2
- Other AE: Items of 1.2.3, 2.1, 2.3, 3.1 and 3.2
- Aquaretic AE: Item 1.1
- Trial too burdensome: Items of 1.2.1 and 1.2.2
- Commercial tolvaptan for ADPKD available: Item 1.3

The reason to map Items of 1.2.3 (Other reasons under Reason other than tolerability) and 3.2 (Subject lost to follow-up) to other AE is for conservativeness to consider them as a reason to be more likely MNAR.

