2.1 Trial Rationale

The current trial will extend the understanding of the efficacy and safety of tolvaptan treatment in ADPKD patients with late stage 2 to early stage 4 CKD. Focusing on the eGFR calculated by the Chronic Kidney Disease-Epidemiology (CKD-EPI) formula (eGFR_{CKD-EPI}, hereafter referred to as “eGFR”)¹¹, this trial is expected to provide kidney function data that are complementary to the data demonstrating the benefits previously observed primarily in ADPKD subjects with earlier stages of disease.

Trial [REDACTED] utilized a post-randomization baseline to account for tolvaptan’s acute hemodynamic effect on eGFR. This hemodynamic effect has been well characterized in prior trials of up to 3-years duration. It has also been examined in subjects with kidney

function ranging from normal to severely dysfunctional due to ADPKD or other disorders.^{12,13} The onset of hemodynamic effect is acute, it persists as long as treatment continues and is rapidly reversible upon discontinuation of treatment. A comparison of tolvaptan and placebo subjects able to complete Trial [REDACTED] indicated that the relative preservation of eGFR during treatment was sustained in the post-treatment follow-up phase and at baseline for Trial 156-08-271 (extending to at least 3 months). In an interim analysis of eGFR in the extension trial, both the prior-placebo and prior-tolvaptan groups exhibited this hemodynamic effect with open-label treatment with differences between groups being sustained for a further 2 years of treatment. (Data on file).

However, in Trial [REDACTED], an early and imbalanced withdrawal of tolvaptan subjects led to missing baseline data for ~5% of tolvaptan subjects, complicating the interpretation of these results. The current trial will utilize tolvaptan treatment titration and tolerability run-in periods to exclude, prior to randomization, those subjects who report they are unlikely to be able to tolerate tolvaptan's aquaretic effects during long-term treatment. This, and a placebo run-in period, will be used to establish a pre-randomization baseline eGFR for each potential treatment assignment, thereby facilitating a straightforward calculation of the key secondary endpoint of eGFR slope for all subjects.

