3.8.3.2 Treatment Interruption

In this year-long trial, it is expected that subjects may have one or more treatment interruptions during the double-blind, randomized treatment period. If a subject’s IMP treatment must be interrupted for medical or surgical reasons; liver test abnormalities; use of a prohibited concomitant medication; or other reasons (eg, hospital admission for an invasive procedure, a major medical condition, surgery; dental work, or a temporary situation that prevents subject compliance with the IMP administration schedule), the subject’s IMP should be resumed as early as the situation allows (see [Section 3.8.3.4](#)).

Any IMP interruption of < 7 consecutive days will be recorded as missed doses rather than as a temporary interruption of IMP. The subject should immediately inform the investigator of any missed doses reaching or expected to be 2 days or more so that the investigator can continue to monitor the subject’s treatments and prepare for a possible 7-day IMP interruption.

An IMP interruption that lasts ≥ 7 consecutive days will be recorded as a “7-day Treatment Interruption” on the eCRF and the subject will visit the clinic to collect vital signs, physical exam, serum creatinine assessment, clinical laboratory assessments, PK/PD samples, and biomarker urine/plasma samples. It is assumed that an interruption of this duration may become permanent, therefore the subject will have a total of 3 samples collected for serum creatinine measurements (in the 2-week period beginning on the 7th day and including the above-mentioned serum creatinine assessment). Treatment may still be restarted during or after these assessments are completed; any remaining serum creatinine assessments will not need to be completed if treatment is restarted during this period. If treatment is restarted, and the subject continues to Month 12, the subject will complete the Month 12 visit and scheduled follow-up assessments; the 7-day Interruption assessments will be considered as unscheduled. This procedure is aimed at ensuring data for the primary endpoint will be collected from all subjects.

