### **5.2 Analysis Data Sets**

The core patient population for all efficacy analyses is based on the intent-to-treat (ITT) population which consists of all randomized subjects who take at least one dose of IMP post-randomization. As will be described below, in order to handle missing and restrictions imposed by different types of analyses (eg, change from baseline analysis), datasets based on modified ITT population will be used in the efficacy analyses.

The Observed Cases (OC) dataset of this protocol is defined as the data observed at study specified visits. For the primary outcome variable of this protocol, the OC dataset consists of the pre-treatment baseline (average of eGFR observed in screening period and the first eGFR observed in placebo run-in period) and post-treatment follow-up (average of eGFR observed in a two-week interval which is one week post the last IMP dose). For the key secondary outcome variable of this protocol, the OC dataset within treatment

period is defined as the data observed at study specified visits while subjects are taking IMP or within 24 hours of the last IMP dose.

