## **8.2 Secondary Outcome Analysis**

### **8.2.1 Key Secondary Endpoint Analysis**

The analysis of the key secondary endpoint will be formally conducted, once the primary endpoint is significant at a two-sided alpha of 0.05. Then a two-sided alpha of 0.05 will be applied to the primary analysis of the key secondary endpoint.

The key secondary endpoint of the trial is the annualized rate of eGFR change, which is derived from each individual subject's eGFR slope using the CKD-EPI formula. Slope is preferred as a practical and clinically meaningful endpoint. In this analysis, all eGFR observations from placebo run-in, tolvaptan run-in (not including tolvaptan titration), double-blind treatment, and post-treatment follow-up (not including data collected in the first week after the last IMP dose) periods will be included in the analysis, with the data of tolvaptan run-in and tolvaptan subjects in the double-blind treatment period are flagged (yes = 1 and no = 0) with a tolvaptan acute hemodynamic effect. The linear mixed effect model with effects of time (as a continuous variable), treatment, time-treatment interaction, acute hemodynamic effect, pre-treatment baseline (of the primary endpoint), and randomization stratification factors will be used to fit the GFR estimates, in which the intercept and time are both a fixed effect and a random effect. An unstructured variance covariance matrix is assumed for the random intercept and time. The time variable used in the model may start from the first observation of eGFR obtained from placebo run-in period. The covariate "acute hemodynamic effect" in the model is the flag variable with value of 0 and 1 specified earlier in this section for the data observed during tolvaptan run-in and the data observed for tolvaptan subjects during the double-blind treatment period. The starting point of this eGFR slope analysis is the eGFR observation during the placebo run-in period.

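### SAP 8.3(7), read literally, codes off-drug interruption values in the tolvaptan arm as still carrying the acute hemodynamic effect

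*SAP*

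**What the plan says.** SAP 8.2.1 fits a linear mixed model to eGFR with treatment, time, their interaction and an acute hemodynamic flag. Tolvaptan run-in data in both arms, and double-blind data of tolvaptan subjects, are "flagged (yes = 1 and no = 0) with a tolvaptan acute hemodynamic effect". The flag is defined again at the end of that section and covers "the data observed for tolvaptan subjects during the double-blind treatment period", with no exception for interruptions. Post-treatment follow-up values after the first off-drug week are also in the model. They are not among the flagged data, so they take 0.

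SAP 8.3(7) deals with tolvaptan subjects who interrupt dosing. Where an eGFR is drawn after more than one week off drug, the stated handling is that "the eGFR observation will be flagged (yes=1 and no = 0) with a tolvaptan hemodynamic effect and included in the key secondary analysis". The next sentence begins "If the observation is less than one week but more than 24 hours from". Values in that window are dropped.

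SAP 5.2 limits the within-treatment observed-cases data for the key secondary outcome to values taken "while subjects are taking IMP or within 24 hours of the last IMP dose".

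On the effect itself, Protocol 2.1 says that "it persists as long as treatment continues and is rapidly reversible upon discontinuation of treatment". On frequency, Protocol 3.8.3.2 says that "it is expected that subjects may have one or more treatment interruptions during the double-blind, randomized treatment period". A subject whose interruption reaches 7 days is to "have a total of 3 samples collected for serum creatinine measurements", in a two-week window that opens on the seventh day, unless dosing restarts first.

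**The concern.** The flag should equal 1 only when the drug's acute effect is present. An eGFR taken more than a week off drug no longer shows the drop. If it is coded 1, the model expects a value 2.6 to 3.4 mL/min/1.73 m² lower than the one it sees. It absorbs that excess partly in the flag coefficient and partly in the tolvaptan slope.

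Three features make this worth settling:

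- The key secondary endpoint is formally tested at two-sided 0.05 once the primary is significant.
- The miscoding can occur only in the tolvaptan arm, so it enters the treatment-by-time term directly.
- Two competent programmers could read the same text and report different estimates. A choice made after unblinding would look driven by the results.

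SAP 5.2 adds a second inconsistency: it restricts within-treatment data to 24 hours after the last dose, while 8.3(7) brings in values more than a week off drug.

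**Working it through.** **What the texts imply for the flag**

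| Tolvaptan-subject value | Off drug | Flag by the text |
|---|---|---|
| Double-blind, on drug | no | 1 (8.2.1) |
| Interruption, 24 h to 1 week | yes | excluded (8.3(7)) |
| Interruption, over 1 week | yes | 1 if 8.3(7) and 8.2.1 are read literally |
| Post-treatment follow-up, after week 1 | yes | 0 (8.2.1) |

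The last two rows describe the same pharmacological state but receive different codes. Other passages support 0 for both. SAP 8.2.2 has the effect starting to reverse within 1 to 2 days, and SAP 5.1 accepts a post-treatment value after one week off drug. Protocol 7.4.2.4 uses the flagging phrase for an on-treatment value, meaning that the effect is present.

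**Reference scale.** 8.3(7) states no figure of its own. The 734 subjects for 90% power in SAP 4.1 cannot be rebuilt because the variances are redacted, but the precision they imply can be backed out:

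- Planned difference: 0.25 × 4.5 = 1.125 per year.
- Implied SE at 734: 1.125 / (1.960 + 1.282) = 0.347.
- At 1300: 0.347 × √(734/1300) = 0.26.

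**Size of the acute effect.** Protocol 1.3 gives 6 to 8%. With the mean baseline of 43.21 in the SAP's sample-size memorandum, 6% is 2.6. The memorandum's tolvaptan run-in mean changes are −3.21 and −3.40 (Rate Blank data). The range used is 2.6 to 3.4.

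**Bias calculation.** The exact expected generalised least squares estimate is

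E(β̂) = (Σ w X′V⁻¹X)⁻¹ Σ w X′V⁻¹μ,

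summed over subject patterns with weights w. X holds intercept, time, treatment, treatment × time and the flag as coded; baseline and strata are left out. μ holds the true acute effect, and the true slope difference is set to zero, so the treatment × time element of E(β̂) is the bias.

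- Visits: Days −36, −8 and −1, Months 1 to 12, follow-up Days 8, 14 and 21.
- Residual variance 7.1 (Protocol 7.1.1); random-intercept variance 120 and slope variance 21 (both assumed).
- 10% of tolvaptan subjects have one interrupted monthly visit (assumed), with true flag 0 coded as 1. The extra-draw case adds two values 5 and 10 days later.

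| Interruptions fall in | Draws | Bias per year, effect 2.6 / 3.4 |
|---|---|---|
| Months 7–12 | one | +0.024 / +0.031 |
| Months 1–6 | one | −0.023 / −0.030 |
| Months 1–12 | one | 0.001 or less |
| Months 10–12 | three | +0.089 / +0.116 |
| Months 10–11 | three | +0.081 / +0.106 |
| Months 1–3 | three | −0.083 / −0.109 |
| Months 1–12 | three | about +0.004 |

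A positive sign favours tolvaptan. A slope variance of 5.27 changes these results by less than 0.003. The bias is about proportional to the share interrupted, so 5% halves it and 20% doubles it.

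Relative to the plan: 0.023/1.125 = 2% and 0.031/1.125 = 3%; 0.116/1.125 = 10%. Against the SE, 0.031/0.26 is about 0.1 and 0.116/0.26 is about 0.4.

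A separate calculation, with a true difference of 1.125, returned exactly 1.125 in every scenario when the interruption values were coded 0.

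**The case against.** The best defence is that 0 was intended. The parenthesis in 8.3(7) names both codes and may be only a coding key. Dropping values between 24 hours and one week makes sense as a washout, which would be pointless if later values were still treated as on drug. And if 8.3(7) meant 1, it would add nothing to 8.2.1. This is persuasive about intent. It does not supply the missing instruction: no sentence assigns 0, and the only explicit definition gives 1.

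On SAP 5.2, one can say that it is a general rule and 8.3(7) a specific exception. That is a fair reading, but the documents do not state it, so at least a cross-reference is needed.

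On size, several limits stand. The extra-draw scenario assumes that subjects stay off drug long enough to give all three samples, although Protocol 3.8.3.2 waives the remaining draws once dosing restarts. It also treats these draws as unscheduled for subjects who restart and reach Month 12, though 8.3(7) does not restrict by visit type. A subject more than a week off drug at Month 12 is arguably in follow-up rather than interrupted. Removing Month 12 and keeping 10% interrupted gives +0.081 to +0.106 instead of +0.089 to +0.116. The early cluster is unaffected. No rate or timing of interruptions is given anywhere.

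**Conclusion.** The concern holds. As written, 8.3(7) together with 8.2.1 gives the wrong covariate value for tolvaptan eGFRs more than a week into an interruption, even though the authors probably meant the opposite.

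The numerical effect is likely small: about 2 to 3% of the planned slope difference if 10% of tolvaptan subjects have one affected visit concentrated in one half of the year, up to about 10% with tight clustering and extra draws, and close to nil if interruptions are spread evenly. The direction depends on timing, so there is no built-in advantage to either arm. These sizes rest on assumed interruption rates and timing and on an acute effect of 2.6 to 3.4.

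The primary endpoint does not use the flag, and the on-treatment Month 1 to 12 MMRM in SAP 8.2.2 is unaffected. The point should be fixed because the analysis is alpha-tested and the text allows two answers. It does not threaten the trial's main conclusion.

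**What to change.** Before unblinding:

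1. In SAP 8.3(7), state that eGFRs more than one week after the last dose before an interruption take flag = 0, as post-treatment follow-up values do.
2. In SAP 8.2.1, add this exception to the definition of the flag.
3. In SAP 5.2, amend the observed-cases definition for the key secondary outcome so that it admits these values.

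If the sponsor prefers to leave 5.2 unchanged, the alternative is to exclude every interruption value beyond 24 hours and to say so in 8.3(7).

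The cost is three SAP sentences and the matching derivation code. No new data are needed.
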